We do not anticipate large amounts of missing data. If the missing data exceeds 5%, sensitivity analyses will be performed using a pattern mixture approach and multiple imputations will be conducted to compare the sensitivity of conclusions to varying assumptions about the missing data, notably whether data are missing at random (MAR) or missing not at random (MNAR) to allow for an assessment of both random and systemic bias. The variation of the primary outcome by different assumptions of missing data will be presented.

Compliance

We will conduct a Complier Average Causal Effects (CACE) analysis using an instrumental variable framework to explore the impact of compliance on the primary outcomes at different levels of compliance. CACE weighs the intention-to-treat (ITT) treatment effect by the proportion of compliance, this allows the estimation of unbiased treatment effects and maintains the allocation in the analysis. The CACE analysis will be implemented using a two-stage least squares (2SLS) approach clustering the standard errors, where the first stage models compliance as a function of the randomised treatment assignment, and the second stage models the outcome as a function of the predicted compliance from the first stage and other covariates.

Compliance will be measured at the school level through a binary variable, compliance (Yes/No). Compliance for those schools in the intervention arm will be assessed based on the level of engagement. Section 5 discusses an engagement tool in more detail. The engagement tool assesses level of schools engagement with the delivery of TISUK intervention across five key dimensions:

- Individual Training,
- Whole Staff Training,
- Consultancy,
- Reflective Supervision,
- Webinars.

Each dimension is scored based on specific criteria, such as the number of staff trained, attendance at meetings, and utilisation of resources. The tool uses a point-based system, with 100 points possible across all dimensions. The final score is calculated as a percentage, with clear thresholds for interpretation:

- up to 50% indicates poor engagement,
- 51-75% moderate engagement,
- 76-90% good engagement, and
- 90-100% excellent engagement.

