	70	0.1272	0.1284	0.1298	0.1317	0.1341
	60	0.1374	0.1385	0.1402	0.1422	0.1449

Rationale for Targeting 100 Schools

Targeting 100 schools and 16,000 students is justified by several considerations. First, a larger pool of schools increases the likelihood of recruiting a diverse population of school types (e.g., school-level of deprivation, FSM, different socioeconomic backgrounds) and student demographics, enabling robust subgroup analyses and generalizability of findings across various contexts. Second, a large overall sample size enhances statistical power to detect smaller but potentially meaningful intervention effects, minimising the risk of false negatives and providing reliable findings to inform future interventions. Third, the target sample size was selected to ensure sufficient power for the quasi-experimental design (QED) analysis focused on a targeted subgroup of students. Lastly, a larger sample size accommodates the cluster randomised trial design, accounting for potential clustering effects and maintaining adequate power for the primary analysis.

Table 4 displays the minimum detectable effect in the protocol according to the assumed parameters, target sample size, and the respective effect size after randomisation driven by the achieved number of responses on the primary outcome. Thus, while the MDES in the protocol is an estimation from the assumptions, the MDES estimated in the column 'Randomisation' corresponds to the actual achieved sample size at baseline in the primary outcome from the schools that were randomised. As we are adopting an intention-to-treat approach, the estimation includes responses from 4 schools that dropped out after randomisation.⁵ Those four schools that dropped out belong to the intervention group.

⁵ This means that now the number of schools in the trial are 74 with 4 dropping out from the intervention group after randomisation

Table 4 Sample size calculations and effects size

		Protocol	Randomisation
Minimum Detectable Effect Size (MDES)		0.1064	0.094
Pre-test/ post-test correlations	level 1 (participant)	n/a	n/a
	level 2 (cluster)	n/a	n/a
Intracluster correlations (ICCs)	level 1 (participant)	n/a	n/a
	level 2 (cluster)	0.03	0.015
Alpha		0.05	0.05
Power		0.8	0.8
One-sided or two-sided?		Two-sided	Two-sided
Average cluster size		160⁶	166⁷
Number of clusters	intervention	50	40
	control	50	38
	Total	100	78 ⁸

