2.3.8 Missing data

The proportion of missing data and patterns of missingness will be examined for the primary outcome only, externalising behaviour at six months post-randomisation. Levels of missing data will be reported along with any systematic occurrences of missing data observed in the dataset.

In trials, some participants are inevitably lost to follow-up. The sample size estimation assumed that 20%¹² of participants would not provide an evaluable 6-month follow-up assessment. We will explore the mechanism of missing data to establish whether the data can be considered missing completely at random or missing at random. For each arm, we will present baseline data for those who were followed up at 6 months and those who were lost to follow-up. A logistic regression analysis will be conducted to explore any systematic differences between the allocated groups. If the regression model does not identify any predictor variables, it suggests that the missing data can be considered missing at random.

To avoid loss of efficiency, missing outcome values will be imputed using multiple imputation if the proportion of missing data is greater than 5% and less than 40%. When less than 5% of data is missing, the proportion is considered negligible, and missing observations will be excluded. Multiple imputation methods may perform less well when a substantial amount of data is missing (e.g., more than 40% for the primary analysis). In such cases, the assumptions underlying the imputation become less plausible, and the interpretative limitations of the trial data will be discussed in the results section.

An initial variable reduction analysis will explore the relationship between all potentially prognostic baseline variables and whether a follow-up data point is missing. Only variables where there is an association (p-value > 0.10) will be included in the imputation model.

The number of imputations will be determined to ensure at least 96% statistical efficiency (RE), according to the formula below, where l is the fraction of missing values and M is the number of repetitions:

$$RE = \left(1 + \frac{\lambda}{M}\right)^{-1}$$

¹² This accounts for 10% attrition and 10% non-consent rate

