The statistical model and assumptions made in the analysis of the primary outcome will also be implemented in the multiple imputation procedures. If it is suspected that data is missing not at random or if the pattern of missing data is associated with trial allocation, sensitivity analysis will be performed using a pattern mixture approach with mixed modelling and multiple imputation to compare the sensitivity of conclusions to varying assumptions about the missing value mechanism.

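### The 96% relative-efficiency rule lets the primary outcome be imputed as few as 2 to 10 times, too few for a borderline imputation p-value to be repeatable across seeds.

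*SAP*

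**What the plan says.** SAP 2.3.8 (Missing data) covers the primary outcome. It states that "missing outcome values will be imputed using multiple imputation if the proportion of missing data is greater than 5% and less than 40" per cent. M is then chosen by relative efficiency: "The number of imputations will be determined to ensure at least 96% statistical efficiency (RE), according to the formula below". The formula is RE = (1 + λ/M)⁻¹, "where l is the fraction of missing values and M is the number of repetitions". The section takes 20% without an evaluable follow-up as its planning figure. Neither document gives a value of M, a higher minimum, a limit on Monte Carlo error, or a random seed.

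The role of the imputed result is described in two ways. SAP 2.3.8 presents imputation as the way to avoid losing efficiency, and keeps the term sensitivity analysis for data suspected to be missing not at random or missing in a pattern linked to allocation. Protocol 4.1 mentions imputation only alongside sensitivity analyses: "If the missing data exceeds 5%, sensitivity analyses will be performed using a pattern mixture approach and multiple imputations will be conducted". SAP 2.3 and 2.3.1 define the primary analysis as a random-intercept model on all available data and do not mention imputation.

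**The concern.** Relative efficiency compares the variance of the estimate from M imputations with that from infinitely many. A figure of 96% sounds strict, but a handful of imputations meets it. It says nothing about whether the standard error, confidence limits and p-value would come out the same under another seed. With few imputations the between-imputation variance is itself poorly estimated, so all three move.

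Imputation is likely to be triggered, because the SAP expects 20% missing and the trigger is 5%. If the imputed result is near p = 0.05, two analysts who both follow the SAP could report it on different sides of the threshold.

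**Working it through.** **Step 1: what the rule requires.** Inputs from SAP 2.3.8: RE ≥ 0.96, λ = fraction missing, imputation window 5% to 40%.

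1/(1 + λ/M) ≥ 0.96 gives λ/M ≤ 1/0.96 − 1 = 1/24, so M ≥ 24λ, rounded up.

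| λ | 24λ | Smallest M | RE at M | RE at M − 1 |
|---|---|---|---|---|
| just above 5% | 1.2 | 2 | 0.976 | 0.952 |
| 10% | 2.4 | 3 | 0.968 | 0.952 |
| 20% (planning figure) | 4.8 | 5 | 0.962 | 0.952 |
| 30% | 7.2 | 8 | 0.964 | 0.959 |
| just below 40% | 9.6 | 10 | 0.962 | 0.957 |

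The plan states no M of its own to reproduce.

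**Step 2: fraction of missing information (FMI).** Seed dependence is governed by the FMI for the treatment effect, which the documents do not give. Two assumptions bracket it.

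(a) FMI equals the fraction missing, which is how the SAP formula treats it: 0.20 at 20% missing.

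(b) Pupils are lost within schools and no school is lost. Then FMI = 1 − [ρ + (1 − ρ)/m] / [ρ + (1 − ρ)/(m(1 − f))], with ρ = 0.015 (baseline ICC, SAP Table 4), m = 13,393/78 ≈ 172 and f = 0.20. Here (1 − ρ)/m = 0.985/172 = 0.00573. The numerator is 0.02073, the denominator is 0.015 + 0.00573/0.8 = 0.02216, and FMI = 1 − 0.935 = 0.065.

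Loss of whole schools moves FMI from (b) towards (a). SAP 2.2 reports that 4 of 78 schools (5.1%), all in the intervention arm, have already dropped out.

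**Step 3: spread of the p-value across seeds.** The simulation repeats the imputations for one fixed data set whose two-sided p would be 0.05 with unlimited imputations. It scales total variance to 1, sets between-imputation variance to FMI, and applies Rubin's rules with Barnard–Rubin degrees of freedom. Complete-data degrees of freedom of 75 (78 schools) are an assumption. The small-sample adjustment moves the stable p only to 0.0504 at FMI 0.065 and 0.051 at FMI 0.20. Repeat runs shift the limits by 0.002 at most.

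| FMI | M | Central 95% of reported p |
|---|---|---|
| 0.065 | 5 | 0.029–0.088 |
| 0.065 | 50 | 0.042–0.059 |
| 0.20 | 5 | 0.017–0.152 |
| 0.20 | 50 | 0.036–0.070 |
| 0.20 | 100 | 0.041–0.064 |
| 0.40 | 10 | 0.015–0.162 |
| 0.40 | 50 | 0.031–0.088 |
| 0.40 | 100 | 0.036–0.076 |

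**Step 4: crossing 0.05.** At FMI 0.065 and M = 5, a stable p of 0.04 is reported as non-significant for about 27% of seeds, and a stable p of 0.06 as significant for about 21%. With M = 50 each falls to about 1%. At FMI 0.20 the figures are about 45% and 29% with M = 5, and about 14% and 10% with M = 50.

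**The case against.** Four points on the other side have force.

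First, a reader might infer that the SAP sets M at 2 to 10. It does not. The 96% is a floor, so a larger M complies. What stands is that nothing requires a larger M, and an analyst who used 5 at 20% missing would be following the plan.

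Second, a reader might infer that analysts with different seeds can reach opposite conclusions on the trial's primary result. The documents do not support that without a condition. The primary model in SAP 2.3.1 uses observed outcomes, and Protocol 4.1 places imputation with the sensitivity analyses. If the mixed model is the headline, the seed cannot touch it. SAP 2.3.8 points the other way, so the role of imputation is unclear rather than settled.

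Third, the ranges above are conditional on a stable p of 0.05, the least favourable point. Averaged over trials the effect is small. With a seed-to-seed SD of z of √(0.065/5) = 0.114, integrating over the sampling distribution of z gives disagreement between two seeds in about 1.5% of trials under the null and 3.6% at 80% power. With SD √(0.20/5) = 0.20 the figures are about 2.8% and 6.3%. These averages use only the variation in the estimate. Rubin's rules already include the finite-M term, and no bias or type I error inflation has been shown. This stands in full: the problem is repeatability of a borderline result, not validity.

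Fourth, a reader might infer that imputing an outcome from the primary model's own covariates gains nothing over the mixed model and adds only noise. That is too strong here. SAP 2.3.8 screens all potentially prognostic baseline variables for the imputation model, so auxiliary variables may enter, recover some information and make missing at random more plausible. The statement that "The statistical model and assumptions made in the analysis of the primary outcome will also be implemented in the multiple imputation procedures" does not exclude them.

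**Conclusion.** The point holds in limited form. That 2 to 10 imputations satisfy the rule, and 5 at 20% missing, is exact arithmetic on the SAP's own formula and window. It is also firm that relative efficiency does not control the repeatability of the p-value.

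The size of the seed effect depends on the assumed fraction of missing information. At 20% missing and M = 5, the reported p for a stable 0.05 spans roughly 0.03 to 0.09 under pupil-level loss only, and 0.02 to 0.15 if the fraction of missing information equals the fraction missing. Fifty imputations narrow these spans considerably but do not remove the spread, least of all when the fraction of missing information is large. A clear result would be little affected. The primary conclusion is exposed only if the imputed analysis is the headline. Because it cannot be known beforehand whether the result will be borderline, M should be fixed before follow-up data are analysed.

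**What to change.** In SAP 2.3.8, replace the 96% rule with a fixed M of at least 50, or 100 if close to 40% of outcomes are missing or whole schools are lost. State the random seed in advance, and report the Monte Carlo error of the estimate and of the p-value. The seed makes a run repeatable; only the larger M reduces the Monte Carlo error.

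Reconcile SAP 2.3.8 with Protocol 4.1 by stating that the mixed model on all observed outcomes is the headline analysis and multiple imputation is a sensitivity analysis.

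The cost is a few sentences in the SAP and a little more computer time. Data collection and design do not change.

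### The protocol requires an MNAR sensitivity analysis of the primary outcome once more than 5% of data are missing; the SAP makes it depend on undefined triggers, so the primary result can be reported without one

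*SAP*

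**What the plan says.** **Protocol 4.1, Missing data.** There is one numeric trigger and no upper limit: "If the missing data exceeds 5%, sensitivity analyses will be performed using a pattern mixture approach and multiple imputations will be conducted". The stated purpose is to compare conclusions under missing-at-random (MAR) and MNAR assumptions. A reporting commitment follows: "The variation of the primary outcome by different assumptions of missing data will be presented".

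**SAP 2.3.8.** Imputation and the pattern-mixture analysis now have separate rules.
- Imputation: "missing outcome values will be imputed using multiple imputation if the proportion of missing data is greater than 5% and less than 40" per cent. Above that level the text says imputation may perform less well and that "the interpretative limitations of the trial data will be discussed in the results section".
- Pattern-mixture analysis: conditional, opening with "If it is suspected that data is missing not at random or if the pattern of missing data is associated with trial allocation". The protocol's promise to present the primary outcome under different assumptions is not repeated.
- Diagnosing the mechanism: baseline data are shown by arm for pupils followed and lost, and a logistic regression is fitted. Then: "If the regression model does not identify any predictor variables, it suggests that the missing data can be considered missing at random".

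The SAP's revision table records only the compliance update, and 2.3.8 does not present its rule as a departure from the protocol. The current versions of both documents are dated July 2024.

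**The concern.** The protocol's trigger can be read off the data. The SAP's two triggers cannot be applied as written.

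- **MNAR suspected.** MAR and MNAR differ in how missingness depends on the unseen values, so observed data cannot separate them. The planned exploration asks only whether data are missing completely at random or at random, so none of its steps can end in MNAR. Finding no predictors of missingness is read as support for MAR, although that result points towards missing completely at random and says nothing against MNAR.
- **Association with allocation.** No test, threshold or level of analysis is given. Similar losses in the two arms can also hide different reasons for loss. That is plausible here: pupils complete the survey in class, and the intervention is meant to reduce exclusions and raise attendance, so it may change which pupils with high externalising scores are present to answer.

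The decision to run the MNAR check would therefore be a judgement made after follow-up data are in hand. A null or small positive primary result could rest on a missing-data assumption that was never varied.

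**Working it through.** **1. The plan's own attrition figure.** SAP 2.2 takes 1,054 pupils and 10% attrition. 527/0.9 = 585.6, so 586 per group and 1,172 in total, as stated. SAP 2.3.8 cites 20%, which its footnote splits into 10% attrition and 10% non-consent. Attrition between baseline and follow-up is therefore 10%.

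**2. Will the 5% level be passed?**
- Assumed attrition alone is 10%.
- Schools already lost: 4 of 40, all intervention (SAP 2.2 and Table 4). With average-sized schools and no follow-up there, 7,214/40 × 4 = 721 pupils, and 721/13,393 = 5.4% of baseline responders (arm sizes from Table 6). Table 4 puts 7,214 in control. If that is right and the intervention arm has 6,179, the share is 4.6%.
- Both together: 10% missing in control and 1 − 0.9 × 0.9 = 19% in intervention. Overall, (0.10 × 6,179 + 0.19 × 7,214)/13,393 = 14.8%.
- With 20% pupil loss instead: 20% and 28% by arm, 24.3% overall.

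**3. Would the allocation trigger fire?** It depends on a test the SAP does not name.
- By school, 4/40 against 0/38: the chance that all four losses fall in the intervention arm is C(40,4)/C(78,4) = 91,390/1,426,425 = 0.064; that all four fall in control, 73,815/1,426,425 = 0.052. Fisher's two-sided p = 0.064 + 0.052 = 0.12.
- By pupil, ignoring clustering, 19% against 10%: z = 0.09/√[0.148 × 0.852 × (1/6,179 + 1/7,214)] = 14.6.

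The same losses give no clear signal on one test and an overwhelming one on the other.

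**4. Size of what is left unchecked.** Inputs from SAP Table 4: ICC 0.015, average cluster size 166, 78 schools. Near-equal allocation gives P(1 − P) = 0.25, and no baseline correlation is used.
- SE = √[(0.015 + 0.985/166)/(0.25 × 78)] = 0.033 SD. With a multiplier of 2.84 on 76 df, the MDES is 0.093, close to the stated 0.094.
- If a share f is missing in each arm, and the between-arm difference among missing pupils departs by δ from what imputation predicts, the estimate shifts by f × δ.

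| Missing share f | δ = 0.1 SD | δ = 0.2 SD | δ = 0.3 SD |
|---|---|---|---|
| 10% | 0.01 (0.3 SE) | 0.02 (0.6 SE) | 0.03 (0.9 SE) |
| 20% | 0.02 (0.6 SE) | 0.04 (1.2 SE) | 0.06 (1.8 SE) |

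Against the MDES, δ = 0.2 is 0.02/0.094 = 21% at 10% missing and 0.04/0.094 = 43% at 20%. The values of δ are assumptions; the documents give none.

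**The case against.** Four objections have force.

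**The 40% limit.** A reader might infer that the SAP stops all sensitivity work above 40%. It does not say so. The 5% to 40% window governs imputation of outcome values, and the pattern-mixture sentence carries no upper limit. Because that analysis is itself to use multiple imputation, its status above 40% is unclear, and unclear is as far as the text goes.

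**Reaching 40%.** A reader might also combine baseline and follow-up losses. Table 6 shows 4,215 of 17,608 baseline scores missing (23.9%), and 1 − 0.761 × 0.8 = 39%. This does not stand. The 20% includes non-consent, and opt-out precedes baseline testing (Protocol section 9), so non-consenters may be counted twice. The window also concerns missing outcomes, not missing baseline and follow-up pairs. With 10% attrition even the pair count is 1 − 0.761 × 0.9 = 31.5%, or 35.2% with the four schools added. Missing follow-up outcomes are 14.8% or 24.3% in the cases worked above. With the four schools lost, reaching 40% would need pupil attrition of 1 − 0.60/0.946 = 37%. The documents do not project that.

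**The triggers may work.** Losing four intervention schools and no control schools may well count as association with allocation. The SAP also speaks of the pattern of missing data, not only its rate, so a different mix of lost pupils could count if it shows in baseline variables. This stands: the MNAR analysis may be run. It is not guaranteed, because no test is set and because loss driven by behaviour after baseline need not show in baseline data.

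**Imputation remains.** Between 5% and 40% the SAP still imputes, so the result is not wholly unexamined. But that imputation follows the primary model's assumptions and does not test them.

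**Conclusion.** The two documents conflict in current text. The SAP turns a required MNAR check into a discretionary one and does not declare the change, so the primary result can be reported without it. That it will be is more than the documents support.

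The protocol's 5% level is very likely, not certain, to be passed. This rests on the assumed 10% attrition and on the four lost schools being of average size and not followed up. The baseline gaps in Table 6 are not follow-up missingness and do not settle the matter.

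The exposure is moderate. At δ = 0.2 SD it runs from about 0.6 SE at 10% missing to 1.2 SE at 20%. That would not overturn a large effect, but it could change the reading of one near the MDES. The figure depends on the assumed δ and on an SE without baseline adjustment; a smaller adjusted SE would make each shift larger in SE units.

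**What to change.** In SAP 2.3.8:

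1. Restore the protocol's rule. If more than 5% of primary outcome data are missing, always report the pattern-mixture (delta-adjusted) analysis, whatever the observed pattern, and present the primary effect across the assumptions.
2. Fix the range of shifts in advance, separately by arm, before outcome data are seen.
3. Remove suspicion of MNAR and association with allocation as conditions. The descriptive work on missingness by arm can stay as context.
4. State that the analysis also applies above 40% missing, and keep 40% only as a caution in interpretation.
5. Record the change in the revision table. If the sponsor prefers the conditional rule, declare it as a departure from the protocol, justify it, and define both triggers.

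The cost is a wording change and a few extra runs of methods both documents already name. The sample size does not change. The downside is a wider reported range for the primary effect.
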